### **Secondary objective**

To compare complications, sedation quality and patient satisfaction.

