Central neuraxial block will be performed under aseptic technique by the anaesthesia medical officer in-charge and the L2-3 or L3-L4 intervertebral space sought with the patient sitting. The subarachnoid space will be located using a pencil 27G (B Braun, Germany) spinal needle and hyperbaric bupivacaine 0.5% plus fentanyl 15-25 µg will be administered. In the case of combined spinal-epidural anaesthesia (CSE), the epidural space will be located with a Tuohy 18G epidural needle, and the epidural catheter secured in place (Espocan®, B Braun, Germany). After establishing an adequate sensory level, surgery will be allowed to proceed, and PCS or TCIS commenced. Patients with failed subarachnoid block or sensory block inadequate for surgery will be dropped out from the study. All patients will receive oxygen supplement of 5L/min via a face mask. Heart rate (HR), blood pressure (BP), oxygen saturation (SpO2) and respiratory rate (RR) will be monitored and documented every 5 minutes. Patients will be kept warm with standard intra-operative warming devices during the surgery.

Propofol will be premixed with lignocaine where 10 mg of lignocaine will be added to every 100 mg propofol 1% to reduce the intensity of pain on injection with propofol. Patients in Group PCS will receive intravenous (IV) propofol (Lipuro® 1%, B.Braun, Germany) via a Graseby® Omnifuse patient controlled analgesia (PCA) (Smith's Medical, UK) infusion pump. The machine will be set to deliver a demand bolus dose of 0.25 mg/kg with no lockout interval or basal infusion. The patient will be instructed to press on a hand-held device as often as required to achieve their desired level of comfort or sedation. The sedation level will be assessed using the Observer's Assessment of Alertness/Sedation Scale (OAA/S; Appendix 2) every 5 minutes in the first 30 minutes, followed by every 20 minutes thereafter.

Patients in Group TCIS will receive IV propofol (Lipuro® 1%, B.Braun, Germany) via a Graseby® Omnifusion target-controlled infusion (TCI) pump (Graseby Medical, Watford,

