U.K) targeting an initial effect site concentration (Cet) of 0.6 µg /ml, using the Schnider pharmacokinetic model. Upon attainment of 0.6 µg /ml Cet, the patient's sedation level will be assessed. The Cet will be increased or reduced accordingly by 0.2 µg/ml to attain an OAA/S score of 3. After equilibrium between predicted and set concentration is achieved, OAA/S score is re-assessed and adjustment of Cet is made until OAA/S score of 3 achieved. The induction time, which is the time taken to reach OAA/S of 3, will be documented in both groups. Thereafter the OAS/S will be assessed every 20 minutes.

Complications from sedation will be managed as follows:

1. Hypotension (systolic BP 20% below baseline) will be treated with administration of IV fluid and titrated bolus doses of IV ephedrine 6 mg or IV phenylephrine 100 µg as required.
2. Bradycardia (HR < 40bpm) will be treated with IV atropine 0.6mg.
3. Respiratory depression (RR < 8 breaths/min) and oxygen desaturation (SpO2 < 95%) will be managed by verbal or tactile stimuli, and titrating down Cet by 0.2 µg/ml in the TCI group, delivering 100% oxygen by applying airway maintenance manoeuvres and assisted ventilation as necessary.
4. Over-sedation (OAS/S score ≤ 2) will be managed by verbal or tactile stimuli, and titrating down Cet by 0.2 µg/ml.

The use of airway adjuncts or intubation will be considered depending on the severity of respiratory compromise. These patients will be excluded from analysis of recovery characteristics.

Sedative administration will be terminated (T0) at the completion of surgery. At the recovery area, standard monitoring will be employed. The medical officer in the recovery room will assess the OAS/S score every 5 minutes. The recovery time, which is the time taken to reach OAS/S 5 from T0 will be documented. Total propofol requirement in both groups will be calculated in mg/kg/hour.

Before discharge from the recovery room, patient satisfaction with sedation was measured using a 10-point verbal rating scale, 1 being extremely dissatisfied and 10 being extremely satisfied.

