### **Statistical tests**

Demographic data and total propofol requirement will be analysed using the student's t-test (or Mann Whitney-U test for non-parametric data). Patients' satisfaction score will be compared using the student's t-test. The satisfaction level of anxious patients in PCS group and TCIS group is compared by using the t-test. A p-value  $< 0.05$  will be considered statistically significant.

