### FLOW CHART

**DATA COLLECTION FORM**

Study ID:					Study group	 PCS  TCIS
Age:		Gender:		Race:		
Height (m):		Weight (kg):		BMI:		ASA:
Diagnosis:				Surgical procedure:		

Time surgery commenced:

Time sedation commenced:

Time to reach OASS score 3: \_\_\_\_\_ min

Time surgery ended:

Time sedation terminated (To):

Total propofol requirement: \_\_\_\_\_ mg

Time of arrival at the recovery room:

Time to reach OASS score 5: \_\_\_\_\_ min

Time discharged from recovery room:

COMPLICATIONS	YES	NO	RESCUE/REMARKS
Systolic BP < 20% baseline			
HR < 40 bpm			
RR < 8/min			
SpO 2 < 95%			
OAS/S ≤ 2			

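### Dropping patients who need an airway adjunct or intubation from the recovery analysis means recovery time is no longer compared between the groups as randomised

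*Combined protocol and SAP*

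**What the plan says.** In Materials and Methods, the list of complications opens with "Complications from sedation will be managed as follows". Directly after the list comes: "The use of airway adjuncts or intubation will be considered depending on the severity of respiratory compromise". The next sentence is: "These patients will be excluded from analysis of recovery characteristics". The natural reading is that patients given an adjunct or intubated are left out. A wider reading, covering everyone with respiratory compromise, is possible and would enlarge the exclusion.

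The same section defines the outcome: "The recovery time, which is the time taken to reach OAS/S 5 from T" (T₀, when sedation stops at the end of surgery). The score is assessed every 5 minutes in the recovery room. The data collection form has a field for T₀ and one labelled "Time to reach OASS score 5".

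Recovery is not a named objective. The secondary objective reads "To compare complications, sedation quality and patient satisfaction". The Statistical tests section gives methods for demographic data, propofol requirement and satisfaction, and none for recovery time. Nothing elsewhere keeps the excluded patients in a recovery analysis, plans a sensitivity analysis or asks for exclusions to be reported by arm.

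**The concern.** Randomisation is described before the patient reaches theatre, and sedation starts only once the block is adequate. The need for an airway adjunct or intubation therefore arises after allocation, and the plan itself groups it with the complications of sedation. Selecting patients on such an event gives up the protection of randomisation for this outcome. The failed-block drop-out is different, because it occurs before study sedation begins.

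The arms could well lose different numbers. PCS is driven by patient demand, "with no lockout interval or basal infusion", while TCIS is titrated by the anaesthetist to an OAA/S score of 3. The decision that triggers exclusion is a judgement of severity made by several medical officers. The documents describe no blinding, and the two delivery systems are visibly different. None of this shows which arm would lose more patients. If the losses differ, a reader of the recovery result could not tell how far, or in which direction, it had moved.

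**Working it through.** **The plan's own figure.** No figure is given for recovery time or for expected exclusions. The only planning figure used here is 39 per group. It reproduces: a two-sided α of 0.05, 80% power, δ = 0.5 and σ = 0.74 give 35 per group by the normal approximation, and 70/0.9 = 77.8, so 78 in total or 39 per group. That calculation concerns propofol requirement; it supplies n and nothing else.

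**Assumed inputs (not in the documents).**
- kP, kT: patients excluded in PCS and TCIS.
- mP, mT: mean recovery time of the other patients in each arm.
- d: how much later excluded patients reach OAA/S 5 than the others in their arm. It may be negative, because recovery is timed from T₀ and not from the airway event.

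**Step 1: difference in means, PCS minus TCIS.**
- With exclusion: mP − mT.
- With all patients: (mP − mT) + d × (kP − kT)/39.

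If the other patients do not differ, exclusion reports 0. The all-patient differences, in minutes, are:

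| Excluded, PCS v TCIS | d = +15 | d = −5 |
|---|---|---|
| 1 v 0 | 15 × 1/39 = +0.38 | −5 × 1/39 = −0.13 |
| 0 v 1 | −0.38 | +0.13 |
| 4 v 1 | 15 × 3/39 = +1.15 | −5 × 3/39 = −0.38 |
| 1 v 4 | −1.15 | +0.38 |
| equal counts, equal d | 0 | 0 |

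If the other patients do differ, say mP = 8 and mT = 10, exclusion reports −2.0 whatever the counts. At d = +15 the all-patient difference is −2 + 1.15 = −0.85 for 4 v 1 and −2 − 1.15 = −3.15 for 1 v 4. Exclusion can therefore enlarge or shrink the difference.

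These figures use observed times for the excluded patients, so they fit patients who needed only an adjunct.

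**Step 2: rank scale, for patients whose time cannot be used.** Give excluded patients the worst rank, count ties as half, and assume no other difference. The probability that a PCS patient recovers faster is then 0.5 + 0.5 × (kT − kP)/39.
- 1 v 0: 0.487
- 4 v 1: 0.462
- 1 v 4: 0.538

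Each unmatched event moves this probability by 0.5/39 = 0.013. With exclusion it stays at 0.50.

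**Step 3: standardised bias and false positives.** Let pP and pT be the proportions excluded, and dP and dT the delays in SD units. Exclusion shifts the difference by −(pP × dP − pT × dT).
- 10% v 0% with d = 1, 2, 3 SD gives −0.10, −0.20, −0.30 SD. Reversing the arms reverses the sign.
- 5% in both arms with dP = 2 and dT = 1 gives −0.05 SD, so equal rates do not guarantee zero bias.

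A simulation used 5,000 trials per setting, 39 per arm, no true difference between the full groups, a t-test, and an assumed correlation of 0.7 between recovery time and a latent exclusion risk. The results were:
- no exclusion: 4.4% false positives
- 10% v 0%: bias −0.13 SD, about 9% false positives
- 0% v 10%: bias +0.14 SD, about 9%
- 5% v 5%: bias about 0, about 5%

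**The case against.** The strongest reply is that little hangs on this. Recovery time is neither a primary nor a secondary objective, has no stated test and does not drive the sample size. Events may also be very few: patients are ASA I or II, and a BMI above 30, sleep apnoea, significant pulmonary disease and features of a difficult airway are all excluded. Four events in one arm is about 10% (4/39) and has no basis in the documents. Even then, the shift on the probability scale is 0.038 against a null standard error of √(79/(12 × 39 × 39)) = 0.066, or about 0.6 standard errors. All of this stands and limits the weight of the point. It does not remove it: the plan defines recovery time, collects it and refers to an analysis of it, and that analysis carries an explicit rule that undoes the randomised comparison.

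A second reply is that recovery time after intubation may mean little. That justifies special handling of intubated patients. It does not justify dropping adjunct-only patients, whose time from T₀ to OAA/S 5 can still be observed.

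A third is that a worst rank merges an airway event with recovery time, and counts again an event already tabulated as a complication. That is fair. Worst rank is a convention, and keeping all sedated patients in the comparison does not depend on it.

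Finally, respiratory compromise may partly reflect the midazolam premedication or the intrathecal fentanyl, which both arms receive. The assigned sedation is therefore a possible cause, not the only one. The exclusion still follows allocation and can still differ by arm.

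**Conclusion.** The concern holds. The plan removes patients from the recovery comparison because of a post-randomisation event that the assigned sedation can cause, and nothing in the documents reverses this. The direction of the bias cannot be fixed from the documents. Over the assumed counts and delays, the shift runs from 0.1 to 1.2 minutes in either direction, or from 0.50 to between 0.46 and 0.54 on the probability scale. It is zero if no such event occurs, or if the excluded patients are equal in number and alike in delay. The event counts, recovery times and correlation are all assumptions. The effect is confined to recovery characteristics; the primary propofol comparison and the complication comparison are untouched. This is a moderate point that should be corrected, with medium confidence in its practical importance.

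**What to change.** Delete the exclusion sentence in Materials and Methods and replace it with a rule on these lines:

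- Compare recovery time (T₀ to OAA/S 5) in all randomised patients who received study sedation.
- Use the observed time wherever OAA/S 5 is observed, including in patients who needed only an airway adjunct.
- Give the worst rank to patients who are intubated or who do not reach OAA/S 5 in the recovery room, and state that this is a convention.
- Report by arm the number of patients given an adjunct, intubated or not reaching OAA/S 5.
- Keep the analysis without these patients as a labelled sensitivity analysis, which also shows whether the worst-rank convention matters.

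Add one line to Statistical tests naming the Mann-Whitney test for recovery time; the section already uses that test for other outcomes.

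The cost is one replaced sentence and one added line. T₀ and time to OAA/S 5 are already on the data collection form. The complications table has no row for an airway adjunct or intubation, only a rescue/remarks column, so a specific entry should be added to make these patients countable. The sample size does not change.

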## **MATERIALS AND METHODS**

This prospective, randomised clinical trial will be submitted for approval from the Research Committee of the Department of Anaesthesiology & Intensive Care, Universiti Kebangsaan Malaysia Medical Centre (UKMMC) and the Medical Research & Ethics Committee, UKMMC. Once ethical approval has been obtained, the subjects will be screened by the principal investigator during the pre-operative visit. Patient inclusion and exclusion criteria include:

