**Appendix 2: Observer's Assessment of Alertness/Sedation (OAA/S) Scale**

Score	Observation
5	Responds readily to name spoken in normal tone
4	Lethargic response to name spoken in normal tone
3	Responds only after name is called loudly and/or repeatedly
2	Responds only after mild prodding or shaking
1	Does not respond to mild prodding or shaking

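### Recovery time rests on one observer's judgement of OAA/S 4 versus 5; no masking is planned, and the form holding the recovery time also shows the study group

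*Combined protocol and SAP*

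**What the plan says.** The recovery paragraph of Materials and Methods (in the text after the exclusion criteria) assigns the scoring: "The medical officer in the recovery room will assess the OAS/S score every 5 minutes". Recovery time is the interval from T0, when sedation stops at the end of surgery, to an OAA/S score of 5. The protocol refers to an analysis of recovery characteristics, from which patients with severe respiratory compromise are left out, so a comparison of the arms is evidently intended.

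In Appendix 2, a score of 4 is "Lethargic response to name spoken in normal tone"; a score of 5 uses the same stimulus with a ready response.

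The design is described only as randomised ("This prospective, randomised clinical trial will be submitted for approval"). Blinding or masking is not mentioned for patients, theatre staff, recovery staff or the analyst.

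The Data Collection Form has PCS and TCIS tick boxes in its header and, lower down, the entry "Time to reach OASS score 5". The Monitoring Chart has an effect-site concentration row marked as applying to the TCIS arm only.

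On satisfaction, the protocol says that before the patient leaves recovery "patient satisfaction with sedation was measured using a 10-point verbal rating scale". It does not name the person who asks.

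**The concern.** An outcome that turns on a fine observer judgement can drift towards what the observer expects when the observer knows the treatment. Here the readings are 5 minutes apart, so one borderline call of 4 instead of 5 moves a patient's recorded recovery time by a whole reading interval. If such calls lean one way in one arm, the comparison of recovery times is biased, and a larger sample would not remove the bias.

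Theatre staff cannot reasonably be masked: one arm uses a hand-set and the other has its target concentration titrated. Recovery is different. Sedation has ended, scoring is already assigned to a recovery-room officer, and the cue on the form can be removed. The plan therefore leaves open a source of bias that it could reduce cheaply.

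**Working it through.** **1. Is the endpoint open to judgement?** Yes. Scores 4 and 5 share one stimulus, the name spoken normally, and differ only in the quality of the response. The step from 4 to 5 is the event that ends recovery time.

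**2. Is the assessor masked?** The documents contain no provision for it.

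**3. Can the assessor learn the arm?** The form that takes the recovery time also displays the group, and the Monitoring Chart has a TCIS-only row. Either would reveal the arm to anyone holding the record. The documents do not say who fills in the form or when, so exposure is easy but not stated as fact.

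**4. Which outcomes are exposed?**
- Recovery time: directly.
- Satisfaction: the patient gives the score. PCS patients operate the button themselves ("The patient will be instructed to press on a hand-held device as often as required to achieve their desired level of comfort or sedation") and so can recognise their technique. Masking the officer cannot blind that rating; it can only limit the influence of whoever asks.
- Primary outcome: not exposed. It is a measured drug amount expressed in mg/kg/hour, and dosing ends at T0, before recovery scoring starts.

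**5. The plan's own sample size.** Inputs from Sample Size Calculation: difference 0.5 mg/kg/hour, SD 0.74, alpha 0.05, power 80%, allocation 1:1. Sidedness is not stated; two-sided is assumed because it reproduces the figure.

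n per group = 2 × (1.960 + 0.842)² × (0.74/0.5)² = 2 × 7.85 × 2.19 = 34.4, rounded up to 35.

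Total with 10% drop-out = 70/(1 − 0.10) = 77.8, rounded up to 78, or 39 per group.

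Both figures reproduce. Masking the recovery assessor would change neither.

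**6. Illustration of what a scoring shift could do.** The assumptions, none of them from the documents, are a two-sided 5% t-test on recovery time (Statistical Tests names no test for it), 35 analysed patients per arm, no true difference, and a systematic shift of b standard deviations between arms caused by scoring alone.

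Non-centrality = b × √(35/2) = b × 4.183, with 68 degrees of freedom. The false-positive rate is the probability that a non-central t variable falls outside the two-sided 5% critical values.

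| Assumed shift b (SD) | Non-centrality | False-positive rate |
|---|---|---|
| 0 | 0 | 5% |
| 0.1 | 0.418 | about 7% |
| 0.2 | 0.837 | about 13% |
| 0.3 | 1.255 | about 24% |
| 0.5 | 2.092 | about 54% |

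The table shows sensitivity to an assumed bias. It does not estimate the bias in this trial.

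**The case against.** The strongest reply is that the plan is silent on masking but does not actually expose the assessor. It does not put the form in the recovery officer's hands. The form has a single summary entry for recovery time, not a series of 5-minute readings, so an investigator could transcribe it later. A reader might infer that the officer necessarily sees the arm while scoring; the documents do not establish that. What stands is that nothing prevents it and that the record as designed makes it easy.

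Four other inferences go too far.

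- **That the form also reveals the arm to whoever records satisfaction.** The form as reproduced has no satisfaction field. One may have been lost when the text was extracted, so its absence is no error, but nothing shows satisfaction being entered under the group box. The rater is in any case the patient.
- **That a separate, uninvolved officer already does the scoring.** The wording suggests this, and several medical officers conduct the study, but no sentence says that the recovery officer had no part in that patient's theatre sedation.
- **That masking would be free.** The form must be split, and the handover, the chart or the patient may still disclose the arm.
- **That biased recovery times would undermine the case for PCS replacing anaesthetist-controlled sedation.** The Introduction rests that case on propofol requirement, safety, sedation quality and satisfaction. Recovery time is not named there or in the objectives, and enters only if read as part of sedation quality.

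The objection on size also stands: the SD, the shift and the test are all assumed.

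**Conclusion.** The point holds in a limited form. Recovery time depends on a subjective call, no assessor masking is planned, and one form carries both the allocation and the recovery-time entry, so the scorer can readily learn the arm. These three facts can be read directly from the documents.

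The size of any bias cannot be derived from them. Under the stated assumptions a shift of 0.2 SD would take the false-positive rate from 5% to about 13%, and the larger values in the table require larger one-directional shifts for which the documents give no evidence.

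The consequence is confined to secondary measures: recovery time directly, and satisfaction only through the way the question is asked. The propofol comparison and the sample size are untouched. This is a worthwhile low-cost improvement, not a threat to the main result.

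**What to change.** 1. Record recovery OAA/S readings and the time to a score of 5 on a separate sheet headed by study ID only, without the group tick boxes and without the TCIS-only concentration row.
2. State in the protocol that the recovery assessor is an officer not involved in that patient's theatre sedation and is kept unaware of the arm where possible, with immediate disclosure whenever care requires it.
3. Name who asks the satisfaction question, give it fixed wording, and state in the report that the patient's rating is itself unblinded.

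**Cost:** a split form and a few protocol sentences. Scoring is already assigned to a recovery-room officer, so no extra staff should be needed, provided that someone other than the theatre officer is available; the site should confirm this. The sample size does not change.

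**Downside:** masking will be partial, because patients or the handover may reveal the arm. The report should say so.

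### Recovery time is counted from T0, but no OAA/S reading is scheduled between T0 and the recovery room, so short recovery times are left-censored at arrival

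*Combined protocol and SAP*

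**What the plan says.** In Materials and Methods (the text after the exclusion criteria), sedation is stopped at T0, "at the completion of surgery. At the recovery area, standard monitoring will be employed". The outcome is then defined: "The recovery time, which is the time taken to reach OAS/S 5 from" T0. The readings described after T0 are these: "The medical officer in the recovery room will assess the OAS/S score every 5 minutes".

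Before T0, both arms are on a sparse schedule by the end of a procedure expected to last 1.5 to 2 hours. For PCS it is "every 5 minutes in the first 30 minutes, followed by every 20 minutes thereafter"; for TCIS, once the target score is reached, "Thereafter the OAS/S will be assessed every 20 minutes". The note under the monitoring chart repeats both schedules and adds no reading at T0.

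The data collection form has fields for T0, for "Time of arrival at the recovery room" and for the minutes to score 5. It has no field for the OAA/S score at T0 or on arrival. Nothing says what to enter for a patient who is already at 5 at the first recovery-room reading.

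Sedation depth is set differently in the two arms. PCS patients press the button "as often as required to achieve their desired level of comfort or sedation", with no OAA/S target. In TCIS, "adjustment of Cet is made until OAA/S score of 3 achieved".

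**The concern.** The clock starts in theatre and the scheduled observer is in the recovery room. A patient who reaches OAA/S 5 before leaving theatre or in transit, or who is already at 5 at T0, has no scheduled reading that could show it. The first opportunity is arrival.

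That the limit applies to both arms does not make it harmless. A common floor cuts off more of whichever arm recovers faster, so the recorded difference shrinks even when transfer times are the same in both arms. Unequal depth at T0 is plausible here, because one arm is titrated to a score of 3 and the other is not. At stake is how a null result on recovery time would be read: it could mean equal recovery, or only that transfer took longer than recovery. Arrival time is recorded, but a true time below it cannot be reconstructed afterwards.

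**Working it through.** **The plan's own figure.** The documents give no figure for recovery time. The only calculation is for propofol requirement: difference 0.5, SD 0.74, alpha 0.05 (taken as two-sided), power 0.80.

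n = 2(1.960 + 0.842)² × 0.74² / 0.5² = 2 × 7.85 × 0.5476 / 0.25 = 34.4, so 35 per arm. With 10% dropout, 70 / 0.9 = 77.8, so 78. Both stated figures reproduce. The 35 per arm is carried into the check below.

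**Recorded time under the written schedule.** Let X be the true time from T0 to OAA/S 5 and A the time from T0 to arrival, with a first reading on arrival and then every 5 minutes:

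recorded = A + 5 × ceil(max(0, X − A) / 5).

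Example with A = 10: patients recovering at 4 and at 8 minutes are both recorded at 10, and their 4-minute difference disappears. A patient recovering at 12 is recorded at 15. With readings every 5 minutes from T0, recorded = 5 × ceil(X / 5).

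**Assumptions (none from the documents).** X is lognormal with log SD 0.5. A has SD 3 minutes and the same distribution in both arms. The test is Mann-Whitney at 0.05. The mean of X is median × exp(0.5²/2) = median × 1.133, so medians of 5 and 8 give 9.07 − 5.67 = 3.4 min, and 10 and 15 give 17.00 − 11.33 = 5.7 min.

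| Medians (min) | Mean transfer (min) | True difference (min) | Recorded (min) | Power as scheduled | Power read from T0 |
|---|---|---|---|---|---|
| 5 vs 8 | 5 | 3.4 | 3.1 | 88% | 93–95% |
| 5 vs 8 | 10 | 3.4 | 2.0 | 51% | 93–95% |
| 5 vs 8 | 15 | 3.4 | 0.8 | 13% | 93–95% |
| 10 vs 15 | 5 | 5.7 | 5.7 | 88% | 88–90% |
| 10 vs 15 | 10 | 5.7 | 5.2 | 85% | 88–90% |
| 15 vs 20 | 10 | 5.7 | 5.6 | 62% | 62% |

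Repeat runs move these by about 0.1 min and one or two percentage points. At 1,500 trials the standard error of a power near 50% is √(0.25/1500) = 1.3 points.

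The cause shows in the share already recovered on arrival. With medians 5 vs 8 and a 10-minute transfer, it is 86% of the faster arm and 62% of the slower.

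**Different model, same pattern.** This version uses a t-test, lognormal times given by mean and SD, and transfer SD 2 min. Means of 5 vs 8 (SD 4) record 2.7, 1.0 and 0.2 min of a true 3.0 at 5, 10 and 15 minutes of transfer. Means of 12 vs 17 (SD 7) record 5.0, 4.5 and 2.8 of a true 5.0.

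**The case against.** **The text forbids nothing.** Recovery time is defined as the time to reach 5, not as the first recovery-room reading, and the theatre officer who already scores OAA/S could note a 5 before transfer. This stands as a limit on wording. A reader might infer that the protocol confines OAA/S to the recovery room and enters the arrival time for anyone already awake. The documents say neither. They schedule no other reading and give no rule. Followed as written, though, the schedule still yields no observation before arrival.

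**The loss may be negligible.** This stands. With recovery medians of 10 minutes or more and a transfer of 5 to 10 minutes, the table shows almost no loss. Showing only fast recovery with slow transfer would give a one-sided picture.

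**The stakes are low.** Recovery time is in neither the primary nor the secondary objective, has no test under Statistical tests and no power target. With equal transfer times the error is toward no difference, so it cannot by itself produce a false advantage for PCS. This rules out a severe reading. The outcome is nonetheless defined and collected, and the protocol refers to an analysis of recovery characteristics.

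**The form helps.** T0 and arrival time allow transfer time to be reported and left-censoring to be applied. They do not supply the missing early times.

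**Theatre scoring is unblinded.** True, and it would bear most on the lighter arm. But the recovery-room officer is not stated to be blinded either, so this is a cost to manage and not a reason to leave the gap.

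**Conclusion.** The concern holds in a limited form. As scheduled, recovery time is left-censored at arrival, and any difference between the arms is attenuated if transfer times are alike in both. The size cannot be fixed from the documents. Under assumed times it runs from almost nothing (medians 10 vs 15 min, transfer 5 min) to most of the effect (medians 5 vs 8 min, transfer 15 min: 0.8 of 3.4 min recorded, power 13%).

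Two stronger conclusions are tempting and not supported. One is that the design hides a faster PCS recovery, or that the outcome mainly measures transfer time. That needs transfer to exceed most recovery times, and the documents give neither; nor do they show that PCS patients are lighter at T0, only that they have no target score. The other is that the trial's main result is at risk. The primary endpoint, its analysis and the sample size do not depend on recovery time. The change is worth making because it is cheap and the lost information cannot be recovered later.

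**What to change.** - Record OAA/S at T0 in theatre (recovery time 0 if already 5), on leaving theatre and on arrival, with no gap longer than 5 minutes until 5 is reached.
- Add fields to the data collection form for the T0 and arrival scores and for who made each score.
- Where the first reading after T0 is on arrival and is already 5, analyse the time as left-censored at arrival (between 0 and the T0-to-arrival interval), not as an exact value.
- Name the recovery-time analysis under Statistical tests, and report transfer time by arm.
- As a sensitivity analysis, report the result from recovery-room scores only.

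The cost is one to three extra scores per patient, a few form fields and a short addition to the analysis text. No treatment changes. The drawback is that the theatre scores are made by an officer who knows the arm; the record of who scored and the sensitivity analysis let a reader judge how much that matters.
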